### **Antitumor Response (RECIST v1.1 Guidelines)**

Antitumor response will be defined as the percent of patients who achieve an objective confirmed response (complete or partial response). Disease control rate (SD for at least 16 weeks or confirmed CR or PR) also will be reported. Response will be determined according to RECIST guidelines. The original RECIST guidelines were developed and published in the Journal of the National Cancer Institute (Therasse, Arbuck et al. 2000).

### **Target Lesion Response (RECIST v1.1 Guidelines)**

Percentage change in SLD will be evaluated by the following formulae:

1. When determining CR or partial response:  
 $(\text{Post value} - \text{Baseline value}) / \text{Baseline value} \times 100$
1. When determining progressive disease:  
 $(\text{Post value} - \text{Nadir value since treatment started}) / (\text{Nadir value since treatment started}) \times 100$

The following definitions will be used to evaluate response based on target lesions at each time point after Baseline:

**Complete Response:** Disappearance of all target lesions.

**Partial Response:** At least a 30% decrease in the SLD of target lesions, taking as reference the Baseline SLD.

**Stable Disease:** Neither sufficient shrinkage of target lesions to qualify for PR, nor sufficient increase to qualify for PD, taking as reference the nadir SLD since the treatment started.

**Progressive Disease:** At least a 20% increase in the SLD of target lesions, taking as reference the nadir SLD recorded since the treatment started, or, the presence of one or more new lesions. In addition to the relative increase of 20%, the sum must also demonstrate an absolute increase of at least 5 mm. The appearance of one or more new lesions is also considered progression. The PET scans will not be used to determine target lesion progression or as a criterion for patient withdrawal from the study. Only CT scans or MRIs will be used for those purposes.

**Not Evaluable (NE):** A target lesion present at Baseline which was not measured, or which was unable to be evaluated leading to an inability to determine the status of that particular tumor for the time point in question. If the SLD cannot be determined at a time point and the rules for PD do not apply, a response of CR, PR, or SD cannot be assigned for that time point, and the time point response will be NE.

**Not Applicable (NA):** No target lesions were identified at Baseline. Patients with no target lesions identified at Baseline cannot be assessed for response. These patients will be assessed for progression only.

**Not Done (ND):** Scans were not performed at this time point to evaluate the target lesions.

### **Non-Target Lesion Response (RECIST v1.1 Guidelines)**

Each non-target lesion will be qualitatively evaluated at each time point. Response of each lesion at each time point will be assessed with respect to the Baseline status. Progression will be assessed with respect to nadir size of the non-target lesions. The overall non-target lesion response for each time point will be assessed as the worst case for the non-target

lesions for that particular time point. If a non-target lesion is classified as NE/ND, the non-target response will be NE/ND unless progression is identified in the available non-target lesions. Response assessments are defined as follows:

**Complete Response:** Disappearance of all non-target lesions, and normalization of tumor marker level. All lymph nodes must be non-pathological in size (< 10 mm short axis) Non-CR/Non-PD: Persistence of one or more non-target lesions and or maintenance of tumor marker level above the normal limits.

**Progressive Disease:** The “unequivocal progression” of existing non-target lesion(s) or appearance of one or more new lesion(s) is considered progressive disease.

**Not Evaluable:** Any non-target lesion present at Baseline which was not measured or was unable to be evaluated leading to an inability to determine the status of that particular tumor for the time point in question.

**Not Applicable:** No non-target lesions were identified at Baseline.

**Not Done (ND):** Scans were not performed at this time point to evaluate the non-target lesions.

**Pseudoprogression:** Patients whose scans show radiographic progression in the absence of clinical deterioration including worsening performance status as assessed by the Investigator may remain on study treatments and additional scan 4 weeks ( $\pm 7$  days) later. If this subsequent scan shows disease progression, the patient will be discontinued from study treatments.

**Response Determination (RECIST v1.1 Guidelines)**

Response at each time point will be assessed as a combination of the target and non-target responses as well as the presence of new lesions according to the table below:

**Time Point Response/Target and Non-Target and Best Response**

Target

| Time Point Response: Patients with Target (±Non-Target) Disease |                             |                    |                         |
|--|-----------------------------|--------------------|-------------------------|
| Target Lesions  | Non-Target Lesions   | New Lesions | Overall Response |
| CR   | CR                          | No                 | CR                      |
| CR   | Non-CR/non-PD               | No                 | PR                      |
| CR   | Not evaluated               | No                 | PR                      |
| PR   | Non-PD or not all evaluated | No                 | PR                      |
| SD   | Non-PD or not all evaluated | No                 | SD                      |
| Not all evaluated  | Non-PD                      | No                 | NE                      |
| PD   | Any                         | Yes or No          | PD                      |
| Any  | PD                          | Yes or No          | PD                      |
| Any  | Any                         | Yes                | PD                      |

Abbreviations: CR = complete response; NE = not evaluable; PD = progressive disease; PR = partial response; SD = stable disease.

Non-Target

| Time Point Response: Patients with Non-Target Disease Only |                    |                         |
|---|--------------------|-------------------------|
| Non-Target Lesions   | New Lesions | Overall Response |
| CR  | No                 | CR                      |
| Non-CR/non-PD   | No                 | Non-CR/non-PD*          |
| Not all evaluated   | No                 | NE                      |
| Unequivocal PD  | Yes or No          | PD                      |
| Any   | Yes                | PD                      |

Abbreviations: CR = complete response; NE = not evaluable; PD = progressive disease.

\* “Non-CR/non-PD is preferred over “stable disease” for non-target disease since SD is increasingly used as endpoint for assessment of efficacy in some trials so to assign this category when no lesions can be measured is not advised.

**Best Overall Response – Confirmation of CR and PR**

| Best Overall Response when Confirmation of CR and PR Required |  |   |
|---|--|---|
| Overall Response First Time Point                             | Overall Response Subsequent Time Point | Best Overall Response   |
| CR  | CR                                     | CR  |
| CR  | PR                                     | SD, PD or PR*   |
| CR  | SD                                     | SD provided minimum criteria for SD duration met, otherwise, PD |
| CR  | PD                                     | SD provided minimum criteria for SD duration met, otherwise, PD |
| CR  | NE                                     | SD provided minimum criteria for SD duration met, otherwise, NE |
| PR  | CR                                     | PR  |
| PR  | PR                                     | PR  |
| PR  | SD                                     | SD  |
| PR  | PD                                     | SD provided minimum criteria for SD duration met, otherwise, PD |
| PR  | NE                                     | SD provided minimum criteria for SD duration met, otherwise, NE |
| NE  | NE                                     | NE  |

Abbreviations: CR = complete response; NE = not evaluable; PD = progressive disease; PR = partial response; SD = stable disease.

\*If a CR is truly met at first time point, then any disease seen at a subsequent time point, even disease meeting PR criteria relative to baseline, makes the disease PD at that time point (since disease must have reappeared after CR). Best response would depend on whether minimum duration for SD was met. However, sometimes 'CR' may be claimed when subsequent scans suggest small lesions were likely still present and in fact the patient had PR, not CR at the first time point. Under these circumstances, the original CR should be changed to PR and the best response is PR.

Source: Eisenhauer, Therasse et al. 2009.

**Appendix E - Hepatic Monitoring Tests for Treatment-Emergent Abnormality**

Selected tests may be obtained in the event of a treatment-emergent hepatic abnormality and may be required in follow-up with patients in consultation with the Lilly CRP.

**Hepatic Monitoring Tests**

---

|   |   |
|---|---|
| 
Hepatic Hematologya
                 Hemoglobin (HGB)
                 Hematocrit (HCT)
                 Erythrocytes (RBC)
                 Leukocytes (WBC)
                 Neutrophilsb
                 Lymphocytes
                 Monocytes
                 Eosinophils
                 Basophils
                 Platelets (PLT)
 
Hepatic Chemistrya
                 Total bilirubin
                 Direct bilirubin
                 Alkaline phosphatase
                 Alanine transaminase (ALT)
                 Aspartate transaminase (AST)
                 Gamma-glutamyl transferase (GGT)
                 Creatine phosphokinase (CPK)
 | 
Haptoglobina
 
Hepatic Coagulationa
                 Prothrombin time (PT)
                 Prothrombin time, INR
 
Hepatic Serologiesa,c
                 Hepatitis A antibody, total
                 Hepatitis A antibody, IgM
                 Hepatitis B surface antigen
                 Hepatitis B surface antibody
                 Hepatitis B Core antibody
                 Hepatitis C antibody
                 Hepatitis E antibody, IgG
                 Hepatitis E antibody, IgM
 
Recommended Autoimmune Serology
                 Anti-nuclear antibodya
                 Anti-smooth muscle antibodya
                 Anti-actin antibodya
 |
|---|---|

---

Abbreviations: CRF = case report form; IgG = immunoglobulin G; IgM = immunoglobulin M; INR = international normalized ratio; RBC = red blood cells; WBC = white blood cells.

- a Assayed by laboratory.
- b Neutrophils reported by automated differential hematology instruments include both segmented and band forms. Whenever a manual differential is needed to report the neutrophils, the segmented and band forms should be added together and recorded on the CRF, unless the CRF specifically provides an entry field for bands.
- c Confirmation dependent on regulatory requirements and/or testing availability.

**(AM0010, pegilodecakin, LY3500518) Indication Studied**

This study is a US only, open-label, randomized, multicenter, Phase 2 second-line trial in adult male and female patients with Stage IV/metastatic NSCLC whose tumors have negative or low expression (0% to 49%) of PD-L1 (without known EGFR mutation or ALK rearrangement) randomized to receive AM0010 in combination with nivolumab or nivolumab alone.

Eli Lilly and Company  
Indianapolis, Indiana USA 46285  
Protocol J1L-AM-JZGD  
Phase 2

Statistical Analysis Plan Version 1 electronically signed and approved by Lilly: 20  
March 2019.

Statistical Analysis Plan Version 2 electronically signed and approved by Lilly on date  
provided below.

Approval Date: 10-Sep-2019 GMT

### 3. Revision History

Statistical Analysis Plan Version 1 was approved prior to the first interim analysis. The first interim analysis was conducted based on data cut-off date: 18 March, 2019

Statistical Analysis Plan Version 2 was approved prior to the first interim analysis. The overall changes and rationale for the changes incorporated in Version 2 are as follows:

- updated to include providing descriptive statistics for the efficacy data at the interim analysis without performing any formal statistical test
- clarified the primary analysis for the primary endpoint objective response rate (ORR) to be based on response assessed per RECIST v1.1; analysis based on confirmed response is added as additional sensitivity analysis for ORR.
- added additional analysis on ORR

Statistical Analysis Plan Version 3 was approved prior to the primary endpoint ORR data lock. The overall changes and rationale for changes incorporated in Version 3 are as follows:

- updated to clarify that the data cut off for the primary analysis of the study will occur at 6 months after the last patient randomized
- clarified that corrected QT interval (QTc) will be calculated based on Fridericia formula

## 4. Study Objectives

### 4.1. Primary Objective

The primary objective of Study J1L-AM-JZGD (JZGD) is to evaluate objective response rate (based on RECIST v1.1) in AM0010 plus nivolumab and nivolumab alone in patients diagnosed with metastatic non-small cell lung cancer (NSCLC) who have been exposed to 1 prior systemic therapy, not containing anti-PD-1/PD-L1 treatment alone, in combination with an anti-CTLA-4 treatment or in combination with platinum-based chemotherapy, and whose tumors have negative or low PD-L1 expression. AM0010 is also known as pegilodecakin and LY3500518 and hereafter is referred to only as AM0010.

### 4.2. Secondary Objectives

The secondary objectives of the study are to estimate AM0010 plus nivolumab versus nivolumab alone with respect to each of the following:

- progression-free survival (PFS)
- overall survival (OS)
- disease control rate (DCR)
- duration of response (DOR)
- safety and tolerability profile

### 4.3. Exploratory Objectives

- To characterize AM0010 pharmacokinetics (PK) in combination with nivolumab
- To explore biomarkers including immune activation markers that may correlate with efficacy outcome measures

[figure not shown]
## 5. Study Design

### 5.1. Summary of Study Design

This is an open-label, randomized, multicenter, Phase 2 second-line trial in adult male and female patients with Stage IV/metastatic NSCLC whose tumors have negative or low expression (0% to 49%) of PD-L1 (without known EGFR mutation or ALK rearrangement). PD-L1 will be determined with any FDA-approved assay detecting PD-L1.

Patients will be stratified according to tumor histology (squamous vs non-squamous) and smoking history (current smoker, former smoker, and never smoker). Current smokers will include subjects with any tobacco use, former smokers will include subjects with a history of tobacco use who do not currently use any tobacco, and never smokers will include subjects who have never used any tobacco products.

- Arm 1: Patients will receive AM0010 and nivolumab
- Arm 2: Patients will receive nivolumab alone

Note: AM0010 is NOT cycle-dependent for either schedule of nivolumab.

Abbreviations: NSCLC = non-small cell lung cancer; PD-L1 = programmed death-ligand 1; Q2W = every 2 weeks; Q4W = every 4 weeks.

Figure JZGD.5.1. Trial and treatment design.

## 5.2. Determination of Sample Size

Approximately 50 patients will be randomized to the 2 treatment arms in a 1:1 ratio. With a total of 50 patients, 25 patients each arm would enable evaluating ORR for each treatment arm. With 25 patients in each treatment arm, the 90% confidence interval (CI) for an objective response rate would be (3%, 28%) if 3 patients (12%) had a response; (11%, 42%) if 6 patients (24%) had a response; and (17%, 50%) if 8 patients (32%) had a response.

## 6. A Priori Statistical Methods

### 6.1. General Considerations

#### 6.1.1. Population

**Enrolled Population:** all patients who signed the informed consent form and were registered into the interactive web response system (IWRS).

**Intent-to-Treat (ITT) population:** all randomized patients per the IWRS.

Unless otherwise noted, all disposition analyses will be performed on the ITT population, all patient characteristic and efficacy analyses will be performed on the ITT population and all safety and exposure analyses will be performed on the safety population.

All analyses will be performed descriptively by treatment arm. Unless otherwise noted, all summary statistics on the ITT population will be performed by assigned treatment arm and all summary statistics on the safety population will be performed by actual treatment received.

**Per-Protocol Population:** all patients who are in the safety population and have no important protocol deviations.

The important protocol deviations which will result in exclusion from the Per-Protocol population are listed below. This is not an exhaustive list and may be amended over the course of the trial.

- patients with disease histology other than NSCLC
- patients with European Cooperative Oncology Group (ECOG) >1 at baseline
- patients who received more than one prior regimen in metastatic setting
- patients who do not have measurable disease at baseline
- patients receiving the incorrect randomized treatment assignment (any amount of duration)

**Response Evaluable Population:** all patients who are randomized and received any amount of study medication, have baseline adequate tumor assessment, and at least 1 post-baseline adequate tumor assessment.

**Safety Population:** all randomized patients who received any amount of study medication, AM0010 or nivolumab.

**PK Population:** all patients who are treated and with available serum time-concentration data from randomized patients.

**Biomarker Population:** all patients who are treated and with available biomarker data from randomized patients.

**ADA Evaluable Population:** all patients who are treated (in safety population), have baseline ADA (Anti-Drug Antibody) result, and at least one post-baseline ADA result.

### **6.1.2. Definitions and Conventions**

Study treatment refers to AM0010 + nivolumab or nivolumab.

The date of randomization is the date the patient was randomly assigned to AM0010 + nivolumab arm or nivolumab arm using the IWRS.

The date of **first** dose is the date of the first dose of any study treatments.

The baseline value of a safety assessment is the last value observed prior to the date of first dose.

The study day of a safety event or assessment will be calculated as:

- The difference between the date of the event or assessment and the date of first study dose plus 1 for all events or assessments occurring on or after the day of first dose. For example, if an event occurs on 08 June 2018 and the date of first dose was 06 June 2018, the study day of the event is 3.
- The difference between the date of the event or assessment and the date of first dose for all events or assessments occurring before the day of first dose. For example, if an event occurs on 05 June 2018 and the date of first dose was 06 June 2018, the study day of the event is -1.

The study day of an efficacy event or assessment will be calculated as:

- the difference between the date of the event or assessment and the date of randomization plus 1 for all events or assessments occurring on or after the date of randomization.
- the difference between the date of the event or assessment and the date of randomization for all events or assessments occurring before the date of randomization.
- 1 month = 30.4375 days
- 1 year = 365.25 days

Unless otherwise noted, summaries of continuous variables will include a mean, median, standard deviation (SD), minimum, and maximum.

Unless otherwise noted, summaries of categorical variables will include the frequency and percentage (relative to the population being analyzed) of each category.

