### **7.3 Screening**

Informed consent must be obtained before any trial specific tests or evaluations are conducted.

The screening visit will occur within 21 days (unless otherwise stated) before administration of trial treatment and may be combined with baseline laboratory evaluations if both are done within 72 hours of initial dosing. Baseline scans for tumor assessment must be performed within 30 days of randomization. Trial eligibility will be based on fulfilling trial inclusion and exclusion criteria. The Investigator will use clinical judgment when determining the clinical significance of laboratory values at baseline and throughout the trial.

At the screening visit, information will be collected, and patients will have clinical evaluations as follows:

- Informed consent
- Demographics
- Medical and cancer history
- Physical examination (including Site/Organ System Status [includes: General appearance, skin, H/E/E/N/T – Thyroid, Pulmonary, Cardiovascular, Gastrointestinal, Musculoskeletal/Extremities, Genitourinary/Breast, Lymph Nodes, Neurological, and Psychiatric]), including height and weight

- Vital signs (5-minute sitting blood pressure, pulse, respiratory rate, oxygen saturation, and oral temperature)
- ECOG performance status assessment
- aPTT and International Normalized Ratio (INR) or PT
- Clinical laboratory tests (hematology, chemistry panel thyroid function (TSH, T3, and T4), and urinalysis)
- 12-lead ECG
- Pregnancy test (urine or serum) in WOCBP
- Radiologic tumor assessment including head and CAPs (within 30 days prior to randomization)
- PD-L1 expression as determined by any FDA-approved PD-L1 assay
- Concomitant medications
- Obtain pathology report of archival tissue.

If screening evaluations are not done within 72 hours of the initial dose of trial drug, the following evaluations will be repeated at a baseline visit:

- Physical examination (Site/Organ System Status [includes: General appearance, skin, H/E/E/N/T – Thyroid, Pulmonary, Cardiovascular, Gastrointestinal, Musculoskeletal/Extremities, Genitourinary/Breast, Lymph Nodes, Neurological, and Psychiatric]), including weight
- Vital signs (5-minute sitting blood pressure, pulse, respiratory rate, oxygen saturation, and oral temperature)
- ECOG performance status assessment
- Clinical laboratory tests (hematology, chemistry panel, coagulation tests, and urinalysis)
- Non-radiologic tumor assessment (if applicable).

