### **7.13 Immunogenicity (Anti-Drug Antibodies)**

Blood samples for immunogenicity analysis will be obtained on all patients on Arms 1 and 2 (including crossover patients). Samples will be evaluated for development of ADAs by a validated immunoassay.

The ADA samples will be drawn pre-dose (AM0010 and nivolumab):

- Day 1 of Cycles 1, 2, 3, 4, and every fourth cycle thereafter (eg, 8, 12, 16, etc.).
- End-of-treatment visit
- Safety observation visits 60 and 90 days after the last dose of study treatment.

For the sample collection during continued-access period, refer Section 3.7 and [Appendix B](#).

All immunogenicity samples will be retained for a maximum of 15 years after the last participant visit, or for a shorter period if local regulations and Ethical Review Boards (ERBs) allow, at a facility selected by the sponsor. The duration allows the sponsor to respond to future regulatory requests related to the investigational product. Any samples remaining after 15 years will be destroyed.

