- c A fresh tissue biopsy is only required if no archival tissue is available within 60 days of informed consent or unless approved by the Medical Monitor.
- d Mandatory tumor tissue sample for biomarker research should be submitted once the patient is enrolled (preferably from the same block used for PD-L1 testing).
- e ADA and PK samples will be collected on Day 1 of Cycles 1, 2, 3, 4, every fourth cycle thereafter, and at end-of-treatment visit, and at the follow-up visits 60 and 90 days after the last dose of study treatment.
- f Biomarker samples will be collected on Day 1 of Cycles 1, 2, 3, 5, 7, 9, 11, etc. and end-of-treatment visits. Specific biomarker blood collection tubes may vary by time point. See the Lab Manual for details.

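### The SAP's baseline rule stops at the day before first dose, so it excludes the Cycle 1 Day 1 pre-dose sample, the only pre-treatment anti-drug antibody (ADA) sample scheduled

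*SAP*

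**What the plan says.** **Baseline rule.** SAP 6.1.2 states: "The baseline value of a safety assessment is the last value observed prior to the date of first dose". The anchor is also a calendar date: the date of first "dose is the date of the first dose of any study treatments". Clock time is not used, and same-day pre-dose values are not excepted. The study-day rule in the same section treats the dosing date as one block, taking the difference in dates "plus 1 for all events or assessments occurring on or after the day of first dose". The SAP's only other baseline statement concerns tumor assessment after crossover (6.7.4).

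**ADA schedule.** Protocol 7.13 lists the sampling days as "Day 1 of Cycles 1, 2, 3, 4, and every fourth cycle thereafter", then end of treatment and the 60- and 90-day visits. On timing it says "The ADA samples will be drawn pre-dose (AM0010 and nivolumab", naming both drugs. Footnote e of Appendix A repeats the days: "ADA and PK samples will be collected on Day 1 of Cycles 1, 2, 3, 4, every fourth cycle thereafter". The screening cell for ADA in Appendix A is empty. Protocol 6.1 starts treatment on trial day 1.

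**ADA population.** SAP 6.1.1 requires that patients "have baseline ADA (Anti-Drug Antibody) result, and at least one post-baseline ADA result". SAP 6.7.3 sets the same condition for its treatment-emergent ADA population and also plans to tabulate patients with ADA present at baseline. Neither section says what baseline means for ADA.

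**Protocol usage.** Protocol 7.2 equates baseline with Day 1. Protocol 7.3 provides for a separate visit: "If screening evaluations are not done within 72 hours of the initial dose of trial drug, the following evaluations will be repeated at a baseline". The list that follows covers physical examination, vital signs, ECOG status and laboratory tests, but not ECG.

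**The concern.** The rule and the sampling schedule do not fit together. The rule wants a value from an earlier date. The schedule supplies the only pre-treatment ADA sample on the dosing date itself.

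Two groups of output depend on this.

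- **Immunogenicity (SAP 6.7.3).** The proportion with treatment-emergent ADA, the proportion with ADA at baseline, and hypersensitivity-type adverse events by ADA status all need a baseline result. The question matters for this drug. Protocol 1.2.2.1 reports that all animals in the 13-week monkey study developed ADA, and protocol 1.2.2.3 reports that ADA positivity lowered exposure in affected monkeys.
- **Laboratory tests, vital signs and ECG (SAP 6.6.7 to 6.6.9).** The value closest to treatment is set aside for an older one. The set-aside value may then be counted as post-baseline. Hemoglobin is the most sensitive case, because reduced red-cell parameters were the predominant monkey finding (protocol 1.2.2.1).

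**Working it through.** The documents give no expected size for the ADA-evaluable population, so there is no planned figure to reproduce. The check applies the SAP's date rule to the protocol's schedule.

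**Step 1. The SAP's own example.** First dose is on 06 June 2018. An event on 08 June is Day 8 − 6 + 1 = 3. An event on 05 June is Day 5 − 6 = −1. Both match SAP 6.1.2.

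**Step 2. The same convention for the first ADA draw.** A Cycle 1 Day 1 pre-dose sample in that patient is dated 06 June. Its study day is 6 − 6 + 1 = 1, in the group on or after first dose. The baseline test asks whether 06 June is earlier than 06 June. It is not, so the sample fails.

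**Step 3. Count of patients with a baseline ADA.** N is about 50 (SAP 5.2). Let q be the share drawn one day early under the ±1 day visit window of protocol 7.1. The documents give no q, so the values below are assumptions. The literal count is q × 50.

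| q (assumed) | Baseline ADA, literal rule |
|---|---|
| 0% | 0 of 50 |
| 2% | 1 of 50 |
| 5% | 2.5, that is 2 or 3 of 50 |
| 10% | 5 of 50 |
| 20% | 10 of 50 |

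These counts come before any loss for missing post-baseline samples.

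**Step 4. Count if same-day pre-dose values are accepted.** Up to 50 of 50 have a baseline. With an assumed share r having a post-baseline result, the evaluable number is r × 50: 50, 45 or 40 for r = 100%, 90% or 80%.

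**Step 5. Does the rule reach ADA at all?** It is worded for safety assessments. Protocol 10.5.4 lists adverse events, physical examinations, vital signs, ECGs and laboratory panels, but not ADA. SAP 6.7.3 sits under exploratory analysis, yet builds its population inside the safety population and uses it to classify adverse events. Either reading is possible. If the rule applies, Step 3 follows. If it does not, no definition exists.

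**Step 6. Laboratory tests, vital signs and ECG.** These are safety assessments on any reading. Appendix A schedules them at screening and on Day 1 of Cycle 1.

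- A value taken on the dosing date is rejected and the previous one is used.
- If screening fell within 72 hours of dosing, the replacement is at most 3 days old.
- At worst it is a screening value 21 days old, counting from trial day 1 (protocol 7.1). Counting from randomization (Appendix A), with treatment starting within 3 days (synopsis), it is 21 + 3 = 24 days.
- Protocol 7.4.1 lets physical examination, weight and laboratory tests be done up to 24 hours before dosing. Those done on the previous date pass the rule. ADA, vital signs and ECG are not named in that allowance.

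**The case against.** The strongest reply is that this is loose wording whose intent is plain. SAP 6.7.3 plans to count patients with ADA at baseline, which presupposes the Cycle 1 Day 1 draw. The protocol calls Day 1 baseline, and a programmer would probably use that sample. The rule may not cover ADA. All analyses are descriptive (SAP 6.1.1), and SAP 6.7.3 sends further immunogenicity work to a separate SAP.

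Much of this stands. It limits the severity and shows that the sample itself is planned. It does not make the rule correct: using the Day 1 sample either departs from the only baseline definition given or fills a gap without authority.

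A reader might also infer more than the documents support:

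- **That no patient at all could have a baseline ADA.** The ±1 day window allows a draw on the day before dosing.
- **That the table of adverse events by ADA status could not be produced.** SAP 6.7.3 runs it on patients who receive AM0010 and includes a group not evaluable for ADA. It could be produced, but nearly everyone would fall in that group.
- **That every Day 1 laboratory value is lost.** Only values dated on the dosing day are.
- **That pre-dose abnormalities must be reported as treatment effects.** The SAP does not define post-baseline. Protocol 10.5.7 restricts its Grade 3 or 4 counts to values after first dose. The risk remains for the SAP's change-from-baseline and worst post-baseline summaries.

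**Conclusion.** The point holds as a defect in the rule's wording and should be fixed. SAP 6.1.2 excludes same-day pre-dose values, and the only scheduled pre-treatment ADA sample is one of these.

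Applied to ADA, the rule leaves 0 of about 50 patients with a baseline, or 1 to 10 if an assumed 2% to 20% were drawn a day early. Accepting same-day pre-dose values gives 40 to 50 evaluable patients, assuming 80% to 100% have a later sample. If the rule is read as not covering ADA, the empty population does not follow, but the definition is missing.

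For laboratory tests, vital signs and ECG, the effect is an older baseline for patients assessed on the dosing date: at worst about 21 days older, and often less. The number of patients affected cannot be derived from the documents.

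Only descriptive safety and exploratory outputs are touched. Objective response rate and the secondary efficacy endpoints are not affected.

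**What to change.** Replace the baseline sentence in SAP 6.1.2 with: *Baseline is the last non-missing value observed before administration of the first dose, including values on the date of first dose. Assessments scheduled as Cycle 1 Day 1 pre-dose are treated as pre-dose if no clock time is recorded.* State that this applies to ADA, laboratory tests, ECG and vital signs.

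Add one line for crossover. First dose in SAP 6.1.2 means any study treatment, so in a patient randomized to nivolumab alone it precedes AM0010. For crossover patients in ADA analyses, use the last ADA result before the first AM0010 dose.

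The cost is a short SAP edit and the matching programming. No new samples, visits or protocol changes are needed.
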